12.2 Sensitivity Analysis for Primary and Key Secondary Efficacy Endpoints

Sensitivity Analysis for the primary and key secondary efficacy endpoints include:

1. All missing data imputed as failure using the FAS
2. Observed data only using the FAS

3. Observed data only using the PPS
4. Missing data will be imputed employing tipping point approach. The analysis will be based on the FAS

For #1, #2 and #3 sensitivity analyses, the analysis of primary and key secondary efficacy endpoints will be performed using a logistic regression model with baseline BDCVA at 40 cm as a covariate and treatment as a main effect. The odds ratio, and 95% confidence interval (CI) for odds ratio will be provided. p-values will be presented for the main effect of treatment group using a Wald statistic.

Tipping Point Analysis of Primary and Key Secondary Efficacy Variables

[figure not shown]
Missing primary and key secondary efficacy endpoint values (i.e., binary response values) will be imputed using tipping point approach. First set all records in CSF-1 with missing value as failures and all records in Vehicle with missing value as successes, that is the worst case. The imputed data will be analyzed using a logistic regression model with baseline BDCVA at 40 cm as a covariate and treatment as a main effect. The p-value, odds ratio, and 95% confidence interval (CI) for odds ratio will be provided. If the p-value is less or equal to 0.05 for the worst case, then stop there. If the p-value is greater than 0.05 for the worst case, then set the missing records as failures or successes in all possible combinations from worse case to the best case until the p-value turns from >0.05 to ≤ 0.05 .

13. Exploratory Analysis

28FEB2022

Confidential & Proprietary

Page 32 of 43

14. Safety Analyses

All safety analyses will be conducted using the SAF. In addition to AEs, BCVA at distance under normal and low-luminance testing conditions, findings from slit-lamp biomicroscopy examination, conjunctival redness grading, study drug drop comfort assessment, dilated indirect fundoscopy, and IOP measurements will be summarized descriptively using quantitative and qualitative summary statistics by treatment arm and subject visit, as appropriate. All such measurements related to safety endpoints will also be presented in a detailed subject listing.

14.1 Adverse Event Summaries

All AEs will be coded using the MedDRA Version 23.0. A treatment-emergent adverse event (TEAE) is defined as any event that has an onset date on or after the first dose of study drug. All AEs collected in the eCRFs will be presented in data listings, but only TEAEs will be summarized in data tables. An overall summary will be presented that includes the number of TEAEs and the number and percentage of subjects who experienced at least one TEAE, by treatment group. This summary will also include breakdowns of TEAEs further categorized as (for ocular and non-ocular separately, where appropriate):

- Ocular TEAEs
- Non-ocular TEAEs
- Ocular Non-Serious TEAEs
- Non-ocular Non-Serious TEAEs
- Most Frequent (> 5% in any arm) Ocular TEAEs
- Most Frequent (> 5% in any arm) Non-ocular TEAEs
- Expected TEAEs
- Unexpected TEAEs
- Suspected treatment-related TEAEs
- All SAEs
- Suspected treatment-related SAEs
- Not Suspected treatment-related SAEs

- TEAEs leading to study discontinuation
- TEAEs by maximal severity
- Suspected Treatment-Related Ocular TEAEs by maximal severity
- Suspected Treatment-Related Non-ocular TEAEs by maximal severity
- Not Suspected Treatment-Related Ocular TEAEs by maximal severity
- Not Suspected Treatment-Related Non-ocular TEAEs by maximal severity

Separate summaries (for ocular and non-ocular, where appropriate) will also be provided for these categories of TEAEs by SOC and PT. If a subject reports the same PT multiple times within the same SOC, that PT will only be reported once within that SOC. As with the PT, if a subject reports multiple conditions within the same SOC, that SOC will only be reported once. In the summary, SOC will be listed in ascending alphabetical order; PTs will be listed in order of descending frequency for CSF-1 treated subjects within each SOC.

All AEs will be presented in a subject listing, with ocular AEs listed separately from non-ocular AEs. All TEAEs leading to study discontinuation will be listed separately. In addition, all SAEs will be presented in a separate listing.

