**Safety Analysis:**

Verbatim descriptions of AEs will be mapped to Medical Dictionary for Regulatory Activities (MedDRA) terms and be presented in a data listing. Treatment Emergent AEs (TEAEs), those that occur after the first Dose of study drug, will be summarized by treatment group using frequency and percent for each System Organ Class (SOC) and Preferred Term (PT) within each SOC. Similar summaries will also be presented for serious TEAEs, TEAEs leading to death, TEAEs leading to study drug discontinuation, TEAEs related to IP and TEAEs by severity. When reporting the incidence of AEs, a subject will only be counted once if they ever experience an event within the SOC and ever experience the individual PT within the SOC.

Actual results and changes from baseline results in monocular and binocular BCVA at 4m and Low- Luminance BCVA, slit-lamp biomicroscopy, conjunctival redness grading, IP drop comfort, IOP, and dilated fundus examination will be summarized descriptively at each visit by treatment group.

Full details of the safety analyses will be specified in the formal SAP.

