**8.6 Subject Disposition**

Completed Subjects

A completed subject is one who has not been discontinued from the study and successfully completes all 4 study visits.

Withdrawn Subjects

A subject may be withdrawn for meeting any of the withdrawal criteria as described in Section [5.3](#).

Discontinued Subjects

A discontinued subject is one who does not complete the protocol-defined study visits. A subject may be discontinued at the discretion of the investigator, sponsor, and/or the Institutional Review

Board (IRB). Notification of early discontinuation from the study and the reason for discontinuation will be made to the sponsor and/or [REDACTED]

Prior to discontinuing a subject, every effort should be made to obtain as much follow-up data as possible, and to retrieve all study materials. AEs will be followed as described in [Section 9](#).

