### **10.8 Safety Analysis**

Verbatim descriptions of AEs will be mapped to Medical Dictionary for Regulatory Activities (MedDRA) terms and be presented in a data listing. Treatment Emergent AEs (TEAEs), those that occur after the first dose of study drug, will be summarized by treatment group using frequency and percent for each System Organ Class (SOC) and Preferred Term (PT) within each SOC. Similar summaries will also be presented for serious TEAEs, TEAEs leading to death, TEAEs leading to study drug discontinuation, TEAEs related to IP and TEAEs by severity. When reporting the incidence of AEs, a subject will only be counted once if they ever experience an event within the SOC and ever experience the individual PT within the SOC.

Actual results and changes from baseline results in monocular and binocular BCVA at 4m and Low- Luminance BCVA, slit-lamp biomicroscopy, conjunctival redness grading, IP drop comfort, IOP, and dilated fundus examination will be summarized descriptively at each visit by treatment group.

Full details of the safety analyses will be specified in the formal SAP.

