The primary objective of this study is to evaluate the efficacy of CSF-1 (0.4% pilocarpine hydrochloride ophthalmic solution) for the temporary correction of presbyopia.

The secondary objectives of this study are to evaluate the safety and tolerability of CSF-1 versus Vehicle.

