8.5 Adjustment for Multiplicity

If the primary null hypothesis, H_{01} , is rejected at a 2-sided alpha = 0.05 in favor of CSF-1 in the alternative hypothesis, H_{11} , tested as delineated in the primary efficacy analysis section ([Section 12.1](#)), then the study will be considered a success and the following key secondary hypotheses will be tested in hierarchical order, each at a 2-sided alpha = 0.05, where inference will be made on each null hypothesis only if the prior null hypotheses are rejected in favor of CSF-1.

1. Visit 3 (Day 8), 2 hours following Dose 1 (H_{02})
2. Visit 3 (Day 8), 1 hour following Dose 2 (H_{03})
3. Visit 3 (Day 8), 2 hours following Dose 2 (H_{04})

9. Disposition of Subjects

Subject disposition will be presented in terms of the numbers and percentages of subjects who were randomized, completed the study, and discontinued from the study. A discontinued subject is someone who does not complete the 4 protocol-defined study visits. Subjects who are not discontinued from the study will be considered study completers. Disposition will be summarized by treatment arm for all randomized subjects. The reasons for study discontinuation will also be summarized and include: AE, lost to follow-up, physician decision, protocol violation, study terminated by sponsor, withdrawal by subject, death, and other. A subject listing will be provided which includes the date and reason for study discontinuation.

The number of subjects in each of the analysis sets (FAS, PPS, and SAF) will be displayed by treatment arm, with the number of subjects and percentages calculated using randomized subjects as the denominator. The number and percentage of subjects with any (major, or minor) protocol deviations will be summarized by treatment arm and overall for all randomized subjects. Protocol deviations will be classified as major or minor prior to the closure of the database during a masked review of each protocol deviation. Major deviations will be defined as those deviations that potentially affect the analysis of the primary study endpoint.

A subject listing will be provided which includes the date of the deviation, the deviation code and description, and the classification of whether the deviation was deemed major or minor. In addition, subject listings will include treatment arm and ICF signature date, and exclusions from the PPS. There will also be a listing of screen failures.

10. Demographic and Baseline Characteristics

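### SAP 14.1 summarises adverse events leading to study discontinuation where the protocol planned study drug discontinuation, so events that made a subject stop the drops but stay in the study are not identified as such

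*SAP*

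**What the plan says.** Protocol 10.8, with the same wording in the synopsis, first plans a TEAE summary by treatment group, SOC and PT. It then promises the same form of summary for several subsets, among them "TEAEs leading to death, TEAEs leading to study drug discontinuation, TEAEs related to IP and TEAEs by severity". It leaves full safety detail to the SAP.

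SAP 14.1 lists 18 TEAE categories, to be shown in an overall summary and again by SOC and PT. The only one concerned with discontinuation is "TEAEs leading to study discontinuation". The dedicated listing follows the same wording: "All TEAEs leading to study discontinuation will be listed separately".

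Both documents define discontinuation by visits. SAP Section 9: "A discontinued subject is someone who does not complete the 4 protocol-defined study visits". Protocol 8.6: "A discontinued subject is one who does not complete the protocol-defined study visits". Under SAP Section 9 everyone else is a study completer.

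The SAP Introduction says that its statistical methods supersede those in the protocol. SAP Section 2 states the objective that these tables serve: "The secondary objectives of this study are to evaluate the safety and tolerability of CSF-1 versus Vehicle".

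**The concern.** Stopping the drops because of an adverse event is one of the most direct signs of intolerance that a two-week eye-drop study can record. The protocol planned to count such events by arm. The SAP's category sounds similar but counts something narrower: events after which the subject left the study. A subject who stopped the drops for an adverse event and still completed Visits 3 and 4 would meet the protocol's category and not the SAP's. What is at stake is one descriptive comparison between the arms, under a stated secondary objective. No efficacy estimate, test or alpha allocation is involved.

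**Working it through.** No figure in the plan depends on this point, so the check is a comparison of texts.

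1. **What is counted.** The synopsis and Protocol 10.8 count TEAEs leading to stopping study drug. None of the 18 categories in SAP 14.1 does so. One counts TEAEs leading to leaving the study.

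2. **Whether the two are the same.** They would be if stopping the drug always meant leaving the study. The documents do not treat them so. In the handling of missing data (Protocol 10.7 and 10.10, SAP 12.1), discontinuation of study drug is one item, ignored under a treatment policy strategy. Withdrawal for lack of efficacy or adverse events is a separate item, imputed as failure. The first item would have little purpose if nobody could stop the drug and still supply data. Protocol 5.3 says that subjects may be withdrawn for an adverse event, not that they must be.

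3. **Which text governs.** The SAP supersedes the protocol's methods. The protocol's deferral to the SAP for full detail explains added detail. It does not explain a narrower category.

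4. **What happens to such a subject under the visible SAP.**
   - Discontinuation category and listing in 14.1: not included, if the four visits are completed.
   - Disposition in Section 9: a completer. Reasons are summarised for study discontinuation only.
   - Safety set (7.3): included, since one dose is enough.
   - Overall, ocular or non-ocular, relatedness, maximal severity and SOC/PT tables, and the listing of all adverse events (14.1): included.
   - Drop comfort (14.5): recorded scores included.

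   What is lost is the identification of the event as one that led to stopping the drops.

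5. **Size.** The documents give an approximate 5% discontinuation rate for the sample size, but no rate of stopping the drops while staying in the study. The number affected therefore cannot be derived. For scale only, one subject in an arm of about 150 is 1/150 = 0.67 percentage points.

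6. **Whether the data would exist.** Protocol 9.1 requires the action taken to be documented for each adverse event. The case report form's response options are not visible.

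**The case against.** The strongest reply is that little is lost. A reader might infer that these subjects vanish from the tolerability tables, or that intolerance as a whole is understated. The documents do not support that: the subjects stay in the safety set, and their events and comfort scores are summarised as set out above. This part of the reply stands and limits the point to one missing attribute of the event.

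Second, SAP Sections 16 (changes from protocol analyses) and 19 (tables) appear as headings without visible content. The change may be declared there, or a table shell may exist. This also stands. The point can be made only about the visible text, and the change cannot be called undeclared.

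Third, the case may be rare. Visits 3 and 4 are built around staff-instilled doses, and the documents do not say whether a subject who attends but declines the drops has completed the visit. That is a fair doubt about frequency. It does not remove the category, because the analysis plan itself provides for drug discontinuation apart from withdrawal.

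Fourth, a reader might infer that deaths are hidden too, since SAP 14.1 has no line for TEAEs leading to death. They are not. A death is a serious adverse event under Protocol 9.2, SAP 14.1 summarises and lists all serious events, and Section 9 tabulates death as a reason for discontinuation.

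**Conclusion.** The point holds in a limited form. The governing document replaces a safety summary planned in the protocol with a narrower one, and under the documents' own definitions the two differ. As the visible SAP is written, TEAEs that led a subject to stop the drops without leaving the study are not identified as such in any described table or dedicated listing. This bears on the tolerability objective and on nothing confirmatory.

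The conclusion assumes that a subject can stop the drops and still count as completing the four visits, which SAP 12.1 implies but no section states outright. It also assumes that the SAP sections without visible content do not already restore the table. A reader might go further and expect a measurable bias against Vehicle. The documents give neither a rate nor a difference between arms from which to calculate one.

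**What to change.** In SAP 14.1, add a category for TEAEs leading to study drug discontinuation, by arm, SOC and PT, with ocular and non-ocular events separate. Keep the existing study-discontinuation category beside it. Derive it from the action-taken item that Protocol 9.1 already requires, after confirming that the case report form records drug discontinuation as a response. If Section 19 already holds such a table, a line in 14.1 naming it is enough.

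The cost is one or two descriptive tables, with no effect on any efficacy analysis. A separate line for TEAEs leading to death would match Protocol 10.8 but is optional, since deaths are already shown elsewhere.

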14.2 Best Distance-Corrected Visual Acuity

Safety variables include BDCVA at 4 m under normal and low-luminance testing conditions.

Monocular BDCVA summaries will specify study eye and fellow eye. Monocular BDCVA and Low-Luminance BDCVA (LL-BDCVA) at 4 m will be measured at pre-treatment, post-Dose 1 and post-Dose 2 as mentioned in the schedule of assessments ([Section 3.2](#)). The observed BDCVA as well as the change from baseline in BDCVA and LL-BDCVA will be summarized by treatment group using continuous descriptive summary statistics, and subject-specific BDCVA and LL-BDCVA data will also be presented in a listing for each visual range, separately. Tables will also provide the number and percentage of eyes that lose 10 or more letters BCDVA at 4 m.

14.3 Slit-Lamp Biomicroscopy Examination

A slit-lamp biomicroscopy examination of the eyelid, conjunctiva, cornea, anterior chamber, iris, and lens will be conducted on both eyes at all scheduled visits pre-treatment, and an End of Visit slit lamp will also be completed at Visit 1 (Day -14 to -1), Visit 2 (Day 1), Visit 3 (Day 8), and Visit 4 (Day 15). Magnification will be consistent with the investigator's standard clinical practice. The subject will be seated for the examination. The results will be graded as normal, abnormal not clinically significant (NCS), or abnormal clinically significant (CS). A table will summarize the findings with frequency counts and percentages for each treatment group at each timepoint and for each eye (study eye and fellow eye). Percentages will be based on the number of subjects in each treatment group with responses. A subject listing of the slit-lamp parameters will also be produced.

14.4 Conjunctival Redness Assessment

Pre-treatment ocular redness will be assessed using the [REDACTED] Scale #6 at Visit 1 (Day -14 to -1), Visit 2 (Day 1), Visit 3 (Day 8), and Visit 4 (Day 15). Post-treatment ocular redness will be assessed at Visit 2 (Day 1), Visit 3 (Day 8) and Visit 4 (Day 15), at 20 minutes, 1 hour post-dose 1, and End of Visit. The [REDACTED] Scale #6 uses the following scoring system:

0 = None

1 = Mild: Slightly dilated blood vessels; color of vessels is typically pink; can be quadrantal

2 = Moderate: More apparent dilation of blood vessels; vessel color is more intense (redder); involves the majority of the vessel bed

3 = Severe: Numerous and obvious dilated blood vessels; in the absence of chemosis the color is deep red, may be less red or pink in presence of chemosis, is not quadrantic

4 = Extremely Severe: Large, numerous, dilated blood vessels characterized by unusually severe deep red color, regardless of grade of chemosis, which involves the entire vessel bed

Conjunctival redness grades and changes from baseline will be summarized by treatment group, for the study eye and fellow eye separately, using continuous descriptive summary statistics. At each post-treatment timepoint, proportions of subjects who are Grade 0 (None) and Grade ≤ 1.0 will be summarized by count and percentage. The results of the conjunctival redness assessments will also be presented in a subject listing.

14.5 Study Drug Drop Comfort Assessment

Study drug drop comfort will be assessed for each eye immediately upon instillation, 30 seconds, and at 1, 5, and 10 minutes post-treatment at Visit 2 (Day 1), Visit 3 (Day 8), and Visit 4 (Day 15) using the [REDACTED] Scale. Subjects will subjectively evaluate their own level of ocular comfort and score according to the following 0-10 scale:

Study drug drop comfort scores will be summarized by treatment group, for the study eye and fellow eye separately, using continuous descriptive summary statistics. At each post-treatment timepoint, the proportions of subjects whose scores are 0, ≤ 1 , and ≤ 2 will be summarized by count and percentage. The results of the study drug drop comfort assessments will also be presented in a subject listing.

14.6 Intraocular Pressure

Intraocular pressure will be assessed via Goldmann applanation tonometry at Visit 1 (Day -14 to -1), Visit 2 (Day 1), Visit 3 (Day 8), and Visit 4 (Day 15). Results will be taken from a single measurement and will be recorded in mmHg. The IOP values and changes from baseline for each eye (study eye and fellow eye) will be summarized using continuous descriptive statistics by visit and eye for each treatment group. A subject listing of IOP results will also be produced.

14.7 Dilated Indirect Fundoscopy

Dilated indirect fundoscopy will be performed at Visit 1 (Day -14 to -1) and Visit 4 (Day 15) using indirect ophthalmoscope. Dilated indirect fundoscopy should always be performed after IOP and all other ocular examinations.

Dilated Indirect fundoscopy parameters collected for the left and right eyes include, vitreous, retina, macula, choroid, and optic nerve. Each parameter is rated "Normal," "Abnormal (NCS)," or "Abnormal (CS)." The subject listing of dilated indirect fundoscopy will include all ratings collected for each parameter in both eyes and the investigator's findings associated with each parameter at each timepoint.

15. Interim Analyses

An interim analysis is not planned for this study.

16. Changes from Protocol-Stated Analyses

[figure not shown]
17. References

US Federal Register. (1998) International Conference on Harmonization; Guidance for Industry: Statistical Principles for Clinical Trials. Department of Health and Human Services: Food and Drug Administration. Federal Register, Vol. 63, No. 179, September 16, 1998, page 49583. (E9)

[figure not shown]
US Federal Register. (1996) International Conference on Harmonization; Guidance for Industry: Structure and Content of Clinical Study Reports. Department of Health and Human Services: Food and Drug Administration. Federal Register Vol. 61, July 17, 1996, page 37320. (E3)

[figure not shown]
18. Revision History

This SAP v2.0 amendment was issued following SAP v1.0, issued on 22NOV2021.

[figure not shown]

[figure not shown]
19. Tables

20. Listings

21. Figures

Figures may be produced at the discretion of the study sponsor.
